64 women will be recruited from the practices of gynecologists and their colleagues. Inclusion criteria will include being sexually active (either with partner or self), post-menopausal, (without spontaneous menses for at least one year, a non-estrogenized vaginal maturation index and a vaginal pH >4.6); experiencing at least 3 months duration with, at least, significant pain on the Numerical Rating Scale (NRS) 0-10-point scale (0-no pain, 1-3 mild, 4-6-moderate, 7-9-significant, 10-severe pain) from secondary provoked vestibulodynia (SPVD). The pain must be significant enough to cause them distress as measured by Female Sexual Distress Scale-Revised (FSDS-R). A score of ≥ 11 effectively discriminates between women with Female Sexual Distress and no FSD. The pain must be significant enough to affect their sexual function, Female Sexual Function Index (FSFI) with a score of 26 or less and effect their sexual activities noted weekly with the standard Sexual Activities Log (SAL).

The intake pelvic examination, including of the vagina, will be normal for a woman's age and years since menopause.

Subjects may or may not have points of erythema in the vulvar vestibule as is common in women suffering from provoked secondary vestibulodynia.

A subject to be included in the study, must have at least significant (7) or above on the Numeric Rating Scale (NRS) of pain intensity (NRS) during the Q-tip test performed at the initial screening visit. Whereas, the Q-tip test must elicit at least significant pain intensity, visible erythema is not necessary to be included in the study. The descriptive characteristics of the pain will be documented using the standard Vulvovaginal Symptoms Questionnaire (VVSQ).

Inclusion Criteria:

Generally healthy women must meet the following eligibility criteria:

1. For surgically menopausal women, be 20-70 years of age and at least 12 months post menopause.
2. For naturally postmenopausal women, be 40-70 years of age and at least 1 year post menopause (defined as no spontaneous menses for 1 year).
3. In screening their vaginal pH will be 4.6 or greater and their vaginal maturation index will be consistent with vaginal atrophy. Vaginal atrophy is thinning, drying and of the vaginal walls due to having less estrogen in the body.

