5. Have evidence of clinically significant organic disorder on the history and/or physical examination that would, in the opinion of the Investigator, put the patient at risk, prevent the patient from completing the study, or otherwise affect the outcome of the study.
6. Have a history of genital herpes because of the episodic nature of genital herpes and of the known possibility of occurrence of herpetic pain without visible dermatologic manifestations of herpes. Genital herpes and its accompanying genital pain may obscure the source of the genital pain experienced and confound the ability to determine the efficacy of treatment/placebo on endpoint of alleviation of pain in women with SPVD.
7. Have any infection of the genitalia
8. Have lichen sclerosis, lichen planus, contact dermatitis, psoriasis or any inflammatory condition or abrasions of the vulva
9. Have an episiotomy scar in the area where pain is perceived as it may confound the etiology of the perceived pain
10. Have diabetes.

5. STUDY PROCEDURES:

Duration of Study:

Once subjects are screened and enrolled into the study, the duration of participation in the study will be 4 weeks from the beginning of the study to the last visit. Follow up questionnaires will be filled out at 6 weeks and electronically entered or mailed in to your clinical trial gynecologist's study clinic office.

Subjects will be given a written description of the study and possible untoward effects of the protocol. They will sign the IRB-approved informed consent. The schedule and activities of visits will be given to the subject, along with instructions about notification in case of untoward events.

Accepted subjects will be randomized and only a non-participant in the clinical trial will hold the code. Except for subjects who decide to leave the trial because of any adverse reactions (i.e.. irritation), prior to its completion, the code will not be broken prior to the completion of the last subject's protocol.

Study Procedures:

Each and every procedure performed is a standard procedure. These procedures will be performed at a screening visit and each of the three subsequent study clinic visits. Initial screening; week 0, week 2; week 4 . Please note, in addition to study related procedures that a standard of care medical history, including past and current medical history, medications, allergies, height, weight and blood pressure will be taken initially and reviewed for any changes on each study clinic visit.

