Examination: The intake pelvic examination, including of the vulva and vagina, will be normal for a woman's age and years since menopause.

Documentation of Erythema: At each visit, erythema of the vestibule will be noted as "present" or "not present" and its location and that of the Q-tip induced pain entered as a drawing on the study chart, see below. There will be no photographic documentation of subjects.

The Q-tip test will be performed at the initial screening visit and all subsequent clinic visits (week 0, 2 , 4). The Q-tip test is a standardized test and involves palpating the vulvar vestibule with a soft, cotton wool-tipped stick and noting the existence of any pain, its location and intensity. Documentation is then made of both the location and intensity of any pain. The intensity of the pain is rated using a standard Numeric Rating Scale (NRS) of pain intensity where. (0) is no pain; (1-3) is mild pain; (4-6) is moderate pain (7-9) is significant pain and (10) is severe pain. Upon initial screening the pain intensity must be at least 7 (significant).

Documentation of sites of elicited or provoked pain will be noted on a clock face standardized clock face diagrammatic drawing with 6 o'clock being at the center of the posterior fourchette of the vulvar vestibule.

Assessment of vaginal atrophy: The Vaginal Maturation Index and Vaginal pH together will be used to establish the lack of estrogenic effect on the vaginal epithelium. Weber MA¹, Limpens J, Roovers JP Assessment of vaginal atrophy: a review Int Urogynecol J. 2015 Jan;26(1):15-28. . Tucker KM, Godha, Mirkin Archer DF Vaginal pH: a simple assessment highly correlated with vaginal morphology and symptoms in postmenopausal women Menopause. 2018 Mar 5.

Vaginal Maturation Index: Vaginal smears will be taken from the upper one third of the lateral vaginal wall for the Vaginal Maturation Index. The Vaginal Maturation Index quantifies the relative proportion of the vaginal parabasal (P), intermediate (I), and superficial (S) cells presented as % P / % I / % S. Vulvovaginal atrophy or estrogen deficiency will be demonstrated by a high percentage of parabasal cells, some intermediate cells and a paucity of superficial cells.

Vaginal pH: Vaginal pH > 4.6 as indication of atrophy, in the absence of infection or semen, of the vaginal epithelium using standard pH paper. Subjects will be asked not to have intercourse with semen deposited in the vagina 24 hours prior to their clinic study visit.

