6. Risks/Safety Information- The risks of full strength topical Veregen® (15% sinecatechins ointment) are well known and well documented in the accompanying package insert. Veregen® Medigene, (Green Tea ointment, (GTO), 15% sinecatechins) is a topical FDA approved drug (2006) indicated for the treatment of external genital warts, since 2006. The package insert specifies it to be applied to each and every visible wart three times a day. The safety profile for Veregen® has been well established. The application of one ½ inch strand of 10% (diluted Veregen) once daily to the vulvar vestibule does not cause the potential irritation that multiple 0.5cm strands of 15% (full strength Veregen) can cause.

The use of significantly lesser doses of the drug (one ½ inch strand), once a day vs the use of multiple 0.5cm strands three times a day and use of a lower concentration of the study drug 10% sinecatechins will significantly reduce the risk of adverse reactions to the drug as seen in the on-label use of the marketed drug Veregen® 15% sinecatechins. In fact, the use of 10% sinecatechins, ½ inch strand, topically applied, once daily to the vulvar vestibule was found to be soothing, and reduced or eliminated vulvar pain in post-menopausal women with secondary provoked vestibulodynia (SPVD).

In Phase 3 clinical trials, a total of 397 subjects received Veregen® (15% sinecatechins) three times per day topical application for the treatment of external genital and perianal warts for up to 16 weeks.

Local irritation is the main potential side effect and in fact the goal of treatment of external genital warts with full strength Veregen (15% sinecatechins ointment) by simultaneously applying a 0.5cm strand to each and every one of multiple visible genital warts three times daily for up to 16 weeks. The mechanism of action of Veregen in clearing genital warts is unknown. (see package insert for Veregen). It was discovered that the off-labeled use of diluted Veregen (10% sinecatechins ointment) applied as a single ½ inch strand once daily was safe and effective in alleviating the pain from SPVD, as demonstrated in the off-labeled use of Veregen with patients in private practice as also seen with 5% sinecatechins ointment (see US Patent 9750716). The mechanism of action of Veregen for treating secondary provoked vestibulodynia (SPVD) is unknown but may be due to Veregen's (sinecatechins, green tea extract) known action as an antioxidant/anti-inflammatory.

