The power analyses were based on previous research data on the effectiveness of the off label use of dilute Veregen (5% sinecatechins ointment) green tea extract (GTE) for the treatment of significant to severe vulvar pain (Patent US 2016/0271102 A1).

Statistical Analyses

Participants randomized to the dilute Veregen (10% sinecatechins ointment) green tea extract (GTE) arm will be compared to those randomized to placebo arm on demographic, descriptive and clinical variables at baseline using chi-square analysis for categorical variables, Student t test and ANOVA test for parametric data and Mann-Whitney U test for nonparametric data.

The ordinal variables (scores from the FSFI, Sexual Distress Scale revised, and the Sexual Activity Log questionnaires) will be analyzed using ANOVA test.

The nominal variables (binary categories from the Vulvovaginal Symptom Questionnaire, Erythema presence/absence and the Sexual Activities Log) will be analyzed using chi-square test. The p-values of less than 0.05 will be considered as statistically significant. These measures will be analyzed at the following assessment points (baseline, 2-week visit, 4-week visit, and 6-week follow-up).

10. IRB Review/Ethics/Informed Consent: Please see attached Informed Consent Document submitted.

IRB Review/Ethics/Informed Consent

This study will be conducted in accordance with the ethical principles that have their origin in the Declaration of Helsinki and that are consistent with Good Clinical Practice and applicable regulatory requirements. The study will be conducted in accordance with the regulations of the United States Food and Drug Administration (FDA) as described in 21 CFR 50 and 56 [add 312 for IND studies or 812 for device studies], applicable laws and the IRB requirements.

The Sponsor will submit any change to the protocol to the IRB for review and approval before implementation. A protocol change intended to eliminate an apparent immediate hazard to subjects will be implemented immediately provided the FDA and the reviewing IRB are notified within 10 working days.

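### Erythema is analysed as one present/absent proportion that ignores baseline status, so cleared and new redness are pooled and the result cannot be assigned to efficacy or tolerability

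*Combined protocol and SAP*

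**What the plan says.** - **Analysis.** Section 9, Statistical Analyses: "The nominal variables (binary categories from the Vulvovaginal Symptom Questionnaire, Erythema presence/absence and the Sexual Activities Log) will be analyzed using chi-square test". The threshold follows: "The p-values of less than 0.05 will be considered as statistically significant". No baseline status, location or direction of benefit is mentioned. I read the test as a comparison between arms at each time point, which the sentence does not spell out.
- **Time points.** Same section: "These measures will be analyzed at the following assessment points (baseline, 2-week visit, 4-week visit, and 6-week follow-up". Erythema falls within that list.
- **Recording.** Section 5, Documentation of Erythema: "At each visit, erythema of the vestibule will be noted as" present or not present, with its location "entered as a drawing on the study chart". No grade or cause is recorded. The clock-face diagram in the same section is specified for sites of provoked pain.
- **Entry.** Section 4: "Subjects may or may not have points of erythema in the vulvar vestibule". The same sentence calls this common in the condition.
- **Possible effects of the drug.** Section 6 offers an anti-inflammatory action as a possible mechanism. It also says "Local irritation is the main potential side effect", but that sentence concerns the full-strength product used on genital warts. Sections 1 and 6 say that the diluted once-daily regimen does not irritate in that way. Section 5 nevertheless plans for irritation, in the instruction sheet and in the rule on breaking the code.
- **Week 6.** Section 5, Duration of Study: "Follow up questionnaires will be filled out at 6 weeks and electronically entered or mailed in". The Week 4 (Visit 3) list describes that visit as the last one in the clinic.

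**The concern.** A woman who is red at baseline can lose her redness; a woman who is not red can acquire it. The first change would suggest benefit and the second would suggest irritation. A single proportion red at week 2 or week 4 adds the two with opposite signs. A difference near zero could then mean that nothing happened, or that both things happened. A difference in either direction would not say which process produced it.

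This matters because erythema is the only local sign seen by an examiner that the Statistical Analyses section names, and that section sets out no analysis of irritation reports. A reader of the results will be inclined to use the erythema comparison as evidence on both benefit and tolerability, and as planned it can serve as neither.

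There is also a smaller mismatch: the time-point list includes a week at which no erythema is recorded.

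**Working it through.** **The plan's own figure.** The documents give no sample size, rate or effect for erythema. The only sample-size figure is for pain: 56 evaluable (28 per arm), raised to 64 for 15% withdrawal. 56 × 1.15 = 64.4 and 56 / 0.85 = 65.9, so 64 is reproduced to within 2 women. I use 28 per arm below.

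**Inputs that are assumptions.**
- *b*, the proportion red at baseline: 30% to 90%
- clearance among women red at baseline: 60% drug, 30% placebo
- new redness among women not red at baseline: 5%, 20% or 35% drug, 5% placebo

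**Formula.** Proportion red after treatment = *b* × (1 − clearance) + (1 − *b*) × new redness.

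Example, *b* = 50%, new redness on drug 35%:
- Drug: 0.5 × 0.4 + 0.5 × 0.35 = 37.5%
- Placebo: 0.5 × 0.7 + 0.5 × 0.05 = 37.5%

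The difference is 0, although clearance differs by 30 points and new redness by 30 points.

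**Range.** The last three columns are rejection rates (%) of the uncorrected chi-square at 0.05, from 20,000 simulated trials with 28 per arm. Small differences in the clearance column at the same *b* are simulation noise.

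| *b* | New redness on drug | Red, drug | Red, placebo | Difference (points) | Pooled test | Clearance, red at baseline | New redness, not red at baseline |
|---|---|---|---|---|---|---|---|
| 30% | 5% | 15.5% | 24.5% | −9.0 | 12.9 | 24.3 | no effect |
| 30% | 20% | 26.0% | 24.5% | +1.5 | 5.2 | 24.6 | 27.3 |
| 30% | 35% | 36.5% | 24.5% | +12.0 | 16.6 | 24.3 | 70.2 |
| 50% | 5% | 22.5% | 37.5% | −15.0 | 23.8 | 36.9 | no effect |
| 50% | 20% | 30.0% | 37.5% | −7.5 | 9.2 | 36.7 | 17.5 |
| 50% | 35% | 37.5% | 37.5% | 0 | 4.6 | 37.2 | 54.0 |
| 70% | 5% | 29.5% | 50.5% | −21.0 | 35.4 | 48.2 | no effect |
| 70% | 20% | 34.0% | 50.5% | −16.5 | 22.7 | 48.2 | 8.3 |
| 70% | 35% | 38.5% | 50.5% | −12.0 | 13.7 | 48.6 | 29.2 |
| 90% | 5% | 36.5% | 63.5% | −27.0 | 51.3 | 58.8 | no effect |
| 90% | 20% | 38.0% | 63.5% | −25.5 | 47.3 | 59.2 | 3.3 |
| 90% | 35% | 39.5% | 63.5% | −24.0 | 42.1 | 58.6 | 8.4 |

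**When the offset is complete.** It requires *b* × (clearance difference) = (1 − *b*) × (new-redness difference). With a 30-point clearance difference, the new-redness difference needed is:
- *b* = 30%: 0.09 / 0.7 = 13 points
- *b* = 50%: 0.15 / 0.5 = 30 points
- *b* = 70%: 0.21 / 0.3 = 70 points
- *b* = 90%: 0.27 / 0.1 = 270 points, which is impossible

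**With no irritation at all.** In the rows with 5% new redness in both arms, the clearance analysis still has more power than the pooled test at every *b* (24.3 against 12.9, up to 58.8 against 51.3). The advantage of splitting does not depend on any offset.

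**Precision after splitting.** At *b* = 50% there are 28 × 0.5 = 14 women per arm in each subgroup. For clearance of 60% against 30%, the approximate 95% half-width is 1.96 × √(0.6 × 0.4/14 + 0.3 × 0.7/14) = 35 points, wider than the 30-point difference itself.

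**Week 6.** Erythema needs an examination. Examinations are at weeks 0, 2 and 4, and week 6 is questionnaires online or by mail. Stray marks in the broken schedule table sit under leftover columns and do not show a week-6 examination. Three of the four listed time points can be analysed.

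**The case against.** The strongest reply is that the offset is hypothetical. The documents give no rate for baseline redness, clearance or new redness. The statement about irritation describes the 15% product applied to multiple warts three times a day, and the protocol says the study regimen does not cause it. This stands. A reader might infer that the drug is known to irritate at the study strength, or that opposite effects will cancel. The documents support neither. What remains is that the protocol's assurance comes from uncontrolled private-practice use, and that section 5 still makes provision for irritation.

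A reader might also infer that real irritation would go unnoticed. That is too strong: subjects are told to notify the gynecologist of irritation, adverse events are reported under section 7, and the code may be broken for women who leave because of irritation.

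It is also fair to say that the split is imperfect and weak. Ointment goes on the painful or reddened areas, so irritation there would be counted as failure to clear. Power is low in every scenario above, and lower still with an exact test. These points call for modest reporting; they do not favour the pooled test, which has the same blind spot and less power for clearance.

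Finally, erythema is not the primary outcome and is not named in the objective. That limits the weight of the point.

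**Conclusion.** The concern holds in a limited form. As written, the plan pools cleared and new redness, and the resulting proportion cannot be assigned to efficacy or tolerability. That follows from mixed entry status and a present/absent comparison that ignores it; it needs no assumed rates.

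The size of any offset does rest on assumed rates. Under those used here it runs from almost nothing (27 to 24 points at 90% red at baseline), through complete (15 to 0 at 50%), to a reversal in sign (−9 to +12 at 30%). The claim that can be defended is that the two effects can partly or fully offset.

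The week-6 entry is a genuine mismatch but a drafting matter: it changes no result. The primary pain comparison is untouched. The amendment is worth making before unblinding because it uses baseline status that is already recorded.

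**What to change.** In section 9, Statistical Analyses, replace the pooled erythema comparison with two secondary analyses. Define baseline as the last examination before the first application.

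1. **Clearance:** the proportion without erythema at week 4 among women with erythema at baseline.
2. **New erythema:** the proportion with erythema at week 2 or week 4 among women without it at baseline, reported as local tolerability beside the irritation reports.

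Give the difference between arms with an exact test or a confidence interval. In women already red at baseline, list erythema at newly drawn locations separately and descriptively; do not add them to analysis 2, where they would blur the denominator. Do not rely on clock positions for erythema, since the protocol specifies only a drawing; a short rule for reading the drawings will be needed.

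Remove erythema from the 6-week assessment point.

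**Cost.** An edit to section 9 and the rule for the drawings, with no new visits or measurements. Each subgroup is small (about 14 per arm if half are red at baseline), so intervals will be wide. Irritation on sites already red will still count as non-clearance, and the report should say so.

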By definition, vestibulodynia, a manifestation of Genito-pelvic Pain/Penetration Disorder, a Female Sexual Disorder must be of significant to severe pain that causes a woman distress with a duration of at least 3 months. The Numerical Rating Scale, pain scale, establishes that they meet the criteria of significant to severe pain to be included in the study. The Vulvovaginal Symptoms Questionnaire characterizes qualities of the pain. The Sexual Distress Scale-Revised demonstrates whether that the pain is significant enough to cause a women distress.

The Female Sexual Function Index corroborates the existence of the pain and its effect on a woman's sexual function in 6 areas: sexual interest, sexual arousal, lubrication, orgasm, satisfaction, and pain. These questionnaires are standard of care. None of these questionnaires are experimental.

No costs will be incurred by the subjects. The Sponsor is funding the costs of the procedures.

Background:

There is no known effective treatment for secondary provoked vestibulodynia and therefore a review of the literature is relevant only to illustrate what has not been effective in alleviating this common human malady. The National Vulvodynia Society and its website contains extensive documentation of the condition and accompanying literature relevant to the epidemiology, characterization and ineffective or marginally effective treatments.

3. OBJECTIVES:

The main objective in this study is to demonstrate whether topical 10% sinecatechins ointment is significantly more efficacious than placebo in alleviating or curing significant to severe vulvar pain due to secondary provoked vestibulodynia, as the most bothersome symptom, in post-menopausal women with evidence of estrogen deficiency (vulvovaginal atrophy) without estrogenic effects on their vaginal epithelium.

4. SUBJECT SELECTION:

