The study medication and placebo have a red brown color and may therefore stain underwear. Subjects will be advised to wear panty liners every day that they apply the study medication in order to avoid staining of their underwear with the medication or placebo.

7. Monitoring and Reporting of Adverse Events/Serious Adverse Events: During the study, if you experience any medical problems, suffer a research-related injury, or have questions, concerns or complaints about the study, please contact your clinical trial gynecologist. If you seek emergency care, or hospitalization is required, alert the treating physician that you are participating in a research study being conducted by your clinical trial gynecologist.

Monitoring of Adverse Events will be done by patients reporting any adverse event to their clinical trial gynecologist. No serious adverse events are expected.

8. Study Oversight: In the unlikely event of the need to prematurely terminate this study of 10% , [name] will be the one to decide to terminate the study. The study will be made available for monitoring, auditing, IRB review and regulatory inspection by providing direct access to study related source data.

9. Data Management- Preliminary Power Analyses and Sample Size Estimates

Power Analyses

For Primary Outcome: Pain Score:

Sample size was calculated to achieve at least 80% power with a significance level of 0.05 using a two-tailed, two-sample t test. A sample size of 56 subjects (28 subjects in treatment group and 28 subjects in the placebo group) was estimated to achieve 80% power to detect at least 2.0-points mean difference between treatment and placebo groups. The Initiative on Methods, Measurement, and Pain Assessment in Clinical Trials suggests that reductions in pain intensity of at least 15–20%, or 2 points in the 0–10 scale, reflect clinically important changes (Dvorkin et al, Core Outcome Measures for Chronic Pain Clinical Trials:

IMMPACT Recommendations Pain: 2005 Jan; 113 (1-2) pp: 9-19)). The pain classification on a 0-10 scale will be as follows: 0 no pain; 1-3 mild pain; 4-6 moderate pain; 7-9 significant pain; 10 severe pain. To compensate for possible withdrawal of 15% of patients in the vulvodynia study, a total sample size of 64 participants (32 in the treatment group, 32 in the placebo group) will be required.

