12. Intended Use of the Data: Should the study confirm the efficacy of 10% sinocatechins ointment (diluted Veregen®) in relieving or curing secondary provoked vestibulodynia in post-menopausal women without any significant effect on the maturation of the vaginal epithelium an excellent option will be available for women who suffer with this life altering condition. It would be a therapeutic option for postmenopausal women especially who because of a past history of gynecologic malignancy would be unwilling or unable to use estrogens A paper may be formulated and presented for publication in the medical literature.

The data is intended to test and therefore confirm the efficacy of local 10% sinocatechins ointment (Green Tea ointment) in the reduction or elimination of secondary provoked vestibulodynia with the added benefits of increasing lubrication and improving sexual function without demonstrable effects on the vaginal epithelium.

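### Six listed outcome measures are tested at several visits at an unadjusted 0.05, with no hierarchy, although the plan intends to confirm added benefits on lubrication and sexual function

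*Combined protocol and SAP*

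**What the plan says.** Section 9 names one primary outcome, the pain score, and sizes the trial for it: "Sample size was calculated to achieve at least 80% power with a significance level of 0.05 using a two-tailed, two-sample t test".

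The Statistical Analyses text then assigns ANOVA to the FSFI, Sexual Distress Scale-Revised and SAL scores, and chi-square to the VVSQ categories, erythema and SAL categories. One threshold follows: "The p-values of less than 0.05 will be considered as statistically significant". The timing is also general: "These measures will be analyzed at the following assessment points (baseline, 2-week visit, 4-week visit, and 6-week follow-up").

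No section gives these measures an order, a priority time point, a multiplicity adjustment or an exploratory label.

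Section 12 (Intended Use of the Data) states that the data are meant to confirm the ointment's efficacy on pain "with the added benefits of increasing lubrication and improving sexual function". Lubrication is one area of the FSFI, which the synopsis describes as covering "sexual function in 6 areas: sexual interest, sexual arousal, lubrication, orgasm, satisfaction, and pain".

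**The concern.** Unadjusted tests on supporting outcomes do little harm when they are reported as description. Here Section 12 announces a confirmatory use for some of them, and Section 9 defines significance without limiting how many results may carry that claim. An analyst who follows the plan exactly could look at three post-baseline times and several overlapping measures of sexual function, and report whichever fell below 0.05. The plan would not show the reader that this was a selection.

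At stake is the credibility of the lubrication and sexual-function statements in any publication. The primary pain test is not affected.

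**Working it through.** **Plan's own figure.** The plan states no overall error rate for these measures, so there is none to reproduce. Its one related calculation, 28 per arm to detect 2.0 points of pain, concerns the primary outcome only. It cannot be rebuilt forwards because no SD is given. Solving backwards with the exact t test gives an SD of about 2.62. Nothing below depends on that value.

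**Count of tests.**
- Questionnaire measures: FSFI score, distress score, SAL score, VVSQ category, SAL category = 5, at weeks 2, 4 and 6: 5 × 3 = 15.
- Erythema is a clinic finding, and week 6 is questionnaires only (Section 5, Duration of Study). That leaves weeks 2 and 4: 2.
- Minimum total: 15 + 2 = 17. Baseline is left out because it cannot produce a treatment claim.

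VVSQ and SAL categories are each counted once. Section 9 uses the plural for VVSQ, so the true count may be higher.

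**If the tests are independent and the ointment does nothing.** Each two-sided test has a 0.05 chance of a false difference and a 0.025 chance of one favouring the ointment.
- Any false difference: 1 − 0.95^17 = 0.582.
- False result favouring the ointment: 1 − 0.975^17 = 0.350.

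**If the tests are correlated.** Repeated visits and overlapping scales will be correlated. The documents give no correlations, so the values here are assumed. Correlated normal test statistics were simulated under the null (400,000 draws), with one correlation between measures and another between visits.

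| Correlation: measures / visits | Any false difference, 17 tests | Favouring the ointment, 17 tests |
|---|---|---|
| 0 / 0 | 58% | 35% |
| 0.3 / 0.5 | 50% | 26% |
| 0.5 / 0.5 | 44% | 23% |
| 0.7 / 0.7 | 32% | 16% |

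**Narrow pool behind Section 12.** Take only FSFI total and FSFI lubrication at weeks 2, 4 and 6: 2 × 3 = 6 tests.
- Independent, favouring the ointment: 1 − 0.975^6 = 0.141. Any direction: 1 − 0.95^6 = 0.265.
- At 0.7 / 0.7: about 9% favouring the ointment and about 18% in any direction.

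**Wide pool.** If the six FSFI areas were tested as well as the total, there would be 12 measures and 12 × 3 − 1 = 35 tests. A false result favouring the ointment would then have a chance of 1 − 0.975^35 = 0.588 if independent, 33% at 0.5 / 0.5 and 22% at 0.7 / 0.7.

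**Benchmark.** One two-sided 0.05 test allows 2.5% in the ointment's favour. Against that, 16% is 6.4 times as large, and the lowest narrow-pool figure, 9%, is 3.6 times as large.

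**The case against.** Several points on the other side are fair.

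- **A false benefit is not shown to be likely.** A reader might take the 58% as the chance of a spurious benefit. It covers differences in either direction, and the chance of one favouring the ointment is 16-35% on the minimum count. With independent tests it passes 50% only from 28 tests (1 − 0.975^28 = 0.508; 27 tests give 0.495). This stands.
- **Not everything measured is tested everywhere.** A reader might infer that every outcome is tested at every visit. Vaginal maturation index and pH are measured but are not in the Section 9 analysis list, and erythema has no week 6 assessment. Calling the listed measures secondary is itself an inference from pain being primary. This stands.
- **Dozens of tests are not written into the plan.** Section 9 refers only to FSFI scores. The six areas describe what the instrument covers, not a stated analysis. The wide pool is therefore a possibility, although a lubrication claim does need at least that one area to be analysed.
- **Section 12 claims only lubrication and sexual function.** Erythema and VVSQ are not part of that claim, so the narrow pool is the fairer measure of that specific risk. This stands, and its 9-14% is still well above 2.5%. Counting SAL as sexual function would raise it.
- **Pain has informal priority.** It is the only outcome called primary, it is the main objective, and the other effects are worded as additions to it. This is priority by emphasis: no rule stops a claim on another measure if pain fails.

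None of these points supplies a multiplicity rule.

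**Conclusion.** The concern holds in a limited form. The plan applies an unadjusted 0.05 to at least 17 post-baseline tests, with no hierarchy, priority time point or formal gate, while intending a confirmatory statement on two supporting effects.

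If the ointment has no effect, the chance of some false significant difference is up to 58% on that count, and of one favouring the ointment up to 35%. Under the assumed correlations these fall to about 32-50% and 16-26%. For the narrow pool that Section 12 most directly needs, a false benefit has a 9-14% chance.

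These figures rest on the minimum count, one test per measure per time point, and assumed correlations of 0.3-0.7 between measures and 0.5-0.7 between visits. If each measure were tested only once overall, the six tests would give 26.5% in any direction and 14.1% favouring the ointment when independent. Error is inflated on every reading, but the documents do not establish that a false benefit is more likely than not.

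**What to change.** In Section 9, replace the blanket 0.05 rule with text along these lines:

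*Before unblinding, one time point and an ordered list of measures supporting secondary claims will be fixed. Each is tested at two-sided 0.05 only if the primary pain test and every earlier step are significant. All other measures and time points are exploratory and are reported as estimates with 95% CI, without significance claims.*

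The choices belong to the sponsor. One example is week 4, the end of treatment, with FSFI total first, then FSFI lubrication, then the distress score. Section 12 should then be limited to claims that survive the order.

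The gate works only if one primary pain test is named. Section 9 says just pain score, while the trial records pain both in a diary and at the Q-tip test, so the rating and the visit must be fixed as well.

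The change needs no extra patients, visits or data. The cost is that fewer supporting results can be called significant. A fixed order keeps 0.05 at each step, whereas a Bonferroni correction over all 17 tests would require p < 0.05/17 = 0.0029.

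Dropping significance tests at baseline is good practice, since differences between randomised arms there are chance, but it is a separate minor point.
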